A pilot intervention trial to reduce the use of post-procedural antimicrobials after common endourologic surgeries

Protocol date March 8, 2024

Version 1.2

Principal investigator: [name], MSc

Data analyst/statistician: [name]; [name], MS; [name]

Urology consultants: [name] and [name]

BACKGROUND

Antimicrobial resistance (AMR) is one of today's most urgent public health problems. Not only is the prevalence of AMR increasing, but the discovery of novel antimicrobial agents has slowed. Infections associated with AMR are more difficult to treat and have worse outcomes than infections due to susceptible pathogens.

Antimicrobial use is a key contributor to the emergence and spread of AMR; therefore, an important target for AMR reduction efforts is unnecessary antimicrobial-prescribing. It is estimated that approximately 30% of all antimicrobial-prescribing is unnecessary.^{1,2} Early efforts to reduce unnecessary antimicrobial-prescribing have largely focused on hospitalized patients and patients in ambulatory care with acute respiratory tract infections.^{3,4}

Opportunities to reduce unnecessary antimicrobial-prescribing in patients undergoing elective ambulatory surgeries have largely gone overlooked. However, several studies describe the extended and often unnecessary use of antimicrobials after ambulatory procedures, including the placement of cardiovascular implantable electronic devices, foot and ankle surgeries, ear/nose/throat surgeries and urologic procedures.⁵⁻⁸

While prolonged post-procedural antimicrobials do not confer any benefit, they do place the patient at increased risk of antimicrobial-related harm, particularly *Clostridioides difficile* infection (CDI). This has been documented in multiple studies across a variety of surgical types, including urologic procedures.^{6,9,10,11}

Audit-and-feedback has been leveraged to reduce the unnecessary use of post-procedural antimicrobials. In 34 hospitals across South Africa, a pharmacist-driven, audit-and-feedback intervention targeted surgeons' compliance with 4 process measures for peri-procedural antimicrobial prophylaxis. The intervention achieved a significant improvement in antimicrobial-prescribing, including a 16.2% improvement in the appropriate duration of peri-procedural antimicrobials.¹² Only 2 of the 34 hospitals audited urologic procedures.

The Surgical Care Improvement Project (SCIP) also used audit-and-feedback to improve antimicrobial-prescribing among surgical inpatients. SCIP was a nationwide initiative to reduce surgical complications through accountability and public disclosure. Ambulatory surgeries and urologic procedures were not included in SCIP. Compliance with SCIP standard 3, the discontinuation of antimicrobials within 24 hours of the operation, increased from <60% at baseline to 94% in 2012.¹³ These improvements were achieved even before CMS tied SCIP measures to hospital reimbursements in fiscal year 2013.

Although audit-and-feedback has been effective in improving antimicrobial-prescribing among certain types of surgical specialties, its benefit among urologic providers is unclear. In 2015, urologists accounted for the 8th highest number of outpatient antimicrobial prescriptions among all specialties.¹⁴ Given such a high frequency of antimicrobial-prescribing, there may be opportunities for enhanced antimicrobial stewardship among urologists.

The Best Practice Policy Statement on Urologic Surgery Antimicrobial Prophylaxis, published by the American Urological Association (AUA), recommends single-dose antimicrobial prophylaxis without post-procedural continuation is recommended for most urologic procedures.¹⁵

However, the unnecessary use of post-procedural antimicrobials is common after urologic procedures, according to administrative data our group analyzed from the VHA. In a national

cohort of nearly 30,000 patients, extended post-procedural antimicrobials (defined as >24 hours) were prescribed after 37.2% of urologic procedures for a median duration of 3.0 excess days.⁵ Based on a manual chart validation, 177 of 211 (83.9%) patients who received excessive post-procedural antimicrobials (i.e. more than 24 hours after the procedure) did not have a clear indication for antimicrobial therapy. At the hospital-level, the use of excessive post-procedural antimicrobials varied widely. For example, after transurethral resection of bladder tumors, the median frequency of excessive post-procedural antimicrobial-prescribing at the hospital-level was 27.9% with an interquartile range of 14.7-55.0%. Overall, we estimate that there are 30,000 days of unnecessary antimicrobial therapy per year in VHA patients undergoing these three urologic procedures.

In a separate study, we found that fluoroquinolones are frequently prescribed for extended surgical prophylaxis in patients undergoing urologic procedures.¹⁶ The frequent use of fluoroquinolones is concerning given the strong association between fluoroquinolone use and several adverse events, including CDI.¹⁷

In December 2018, our study team surveyed 110 hospitals within the research network of the Society for Healthcare Epidemiology of America. Forty hospitals (36.4%) responded. Among the 38 hospitals that performed urologic procedures, 18 (47.4%) had never audited whether urologists at their facility adhered to the AUA guidelines for post-procedural antimicrobial use. In the hospitals that did audit, 30% reported that antimicrobials were always prescribed for more than 24 hours. Another 30% reported prolonged post-procedural courses were prescribed in some patients.

These findings suggest that there is an unrecognized opportunity to evaluate and potentially improve antimicrobial-prescribing in patients undergoing urologic procedures. The following study will leverage audit-and-feedback plus additional implementation strategies with the goal of reducing unnecessary post-procedural antimicrobial use after 3 common urologic procedures. The findings from this pilot trial could inform a larger intervention across the VHA to reduce the use of excessive post-procedural antimicrobial prophylaxis in urologic patients.

METHODS

Trial design:

We will use a before/after quasi-experimental design, which will be analyzed with an interrupted time-series analysis.

Participants:

Eligibility criteria: There will be 3 intervention VHA hospitals. To be eligible, a VHA hospital must perform the following 3 urologic procedures: transurethral resection of the prostate (TURP), transurethral resection of a bladder tumor (TUBRT), and ureteroscopy (URS). Eligible VAMCs needed to perform these three index procedures, perform at least 75 qualifying procedures per year, and utilize excess post-procedural antimicrobial in the highest tertile for all sites.

Method of recruitment: The Chief of Urology at an eligible intervention sites will be contacted by e-mail. A follow-up Microsoft Teams or Zoom call will be scheduled to explain the project, if the Chief of Urology is interested in potentially participating.

Interventions:

- Content: Feedback on the percentage of patients who underwent a qualifying procedure and received an antimicrobial on post-procedural day 1
- Delivery method: At baseline, feedback will be given via a video-conferencing call in which we show the team their feedback report and explain what it means. All subsequent feedback will be delivered through e-mail.
- Unit of delivery: The feedback will be given to all practicing urologists at a site.
- Deliverer: The baseline video-conferencing call will be attended by the study team (Drs. [name], [name] and [name]). The electronic feedback will be sent from the PI's e-mail account.
- Setting: The intervention will be delivered via video-conferencing (baseline) or via e-mail (months 1, 3, 5, 7, 9, and 11).
- Exposure quantity and duration: Feedback will be given at baseline and every 2 months
- Time span: 12 months
- Activities to increase compliance or adherence: During the introductory call, the study team will review the AUA's guidelines on antimicrobial prophylaxis and the potential harms of extending antimicrobial prophylaxis beyond a single dose.^{15,18} The Chief of Urology at each site will be encouraged to be a local champion for more judicious use of post-procedural antibiotics.

Objectives:

- Study objectives: Evaluate whether a pilot audit-and-feedback intervention across 3 hospitals can safely reduce the unnecessary use of post-procedural antimicrobials in patients undergoing urologic procedures.
- Hypotheses: An bundled intervention across 3 hospitals will facilitate safe reductions in post-procedural antimicrobial-prescribing.

Outcomes:

Clinical outcomes are listed below. Data for all clinical outcomes will be extracted from the Corporate Data Warehouse (CDW) using the VA Informatics and Computing Infrastructure (VINCI).

Primary outcome

Excess post-procedural antimicrobial use is defined as a prescription for a designated antimicrobial agent on post-procedural day one. Designated antimicrobials will be antimicrobial agents potentially used for a urinary tract-related indication, as outlined in our prior work.⁵ This definition will be used to minimize the chance of including patients receiving antimicrobials for non-urologic or non-prophylactic indications.

Patients will be eligible for this outcome if they underwent a medical procedure coded with a Current Procedural Terminology (CPT) code or an International Classification of Diseases, 10th version, Procedure Coding System (ICD-10-PCS) code for TURPs, TURBTs, and URSs during

the 2-year baseline period or during the 1-year intervention period. These three procedures were selected because they are all common procedures performed endoscopically with no skin incision required. In addition, for all 3 procedures, the AUA guidelines give a clear recommendation for giving a single dose of antimicrobial prophylaxis.¹⁵

Secondary outcomes

Excess post-procedural antimicrobial duration is defined as the duration of continuous excessive post-procedural antimicrobial use, as quantified as days of therapy per National Healthcare Safety Network methodology.¹⁹

Safety outcomes

- Late antimicrobial prescription is defined as the prescription of a designated antimicrobial that does not qualify as a post-procedural antimicrobial (see above) by any provider within 7-30 days of the date of the patient's urologic procedure. All late antimicrobial prescriptions must be agents potentially used for a urinary tract-related indication, as outlined in our prior work.⁵
- Return visits: seeking care in an Emergency Department, Urgent Care Clinic or hospital readmission to an acute-care bed at a VHA facility for any indication within 30 days of the patient's index urologic procedure.

Assignment Method: Intervention sites will be selected from the top tertile of all sites, as ranked on the frequency of excess post-procedural antimicrobial-prescribing. Eligible new sites will be invited until 3 unique sites agree to participate.

Sample Size: This was a pilot trial, so no sample size calculation was performed.

Blinding: None

Unit of Analysis: Each medical center (3 intervention)

Statistical Methods:

Patient demographics, comorbidities, and types of procedures are presented by count and percentages. Observations occurring within the implementation phase (July 2022) were omitted from all analyses. Observations from each of the three sites were stratified into three data sets to accommodate separate analyses on each site.

To model the primary outcome, we used a logistic regression model and a set of three explanatory variables: time, a binary indicator for an observation occurring within the intervention phase, and an interaction term between these two main effects (time and intervention). Time was measured in days divided by 365, giving an annualized figure for the time coefficient estimate and interaction coefficient. In the tables of results of these logistic regression models, the coefficient estimates are exponentiated to display estimated multiplicative effect on the odds; 95% confidence intervals are also provided on the odds scale. The median duration of post-procedural antimicrobial prescriptions at each site were compared using the Wilcoxon rank-sum test.

To model the secondary outcomes, we used a similar approach to what is described above with the addition of a fourth explanatory variable (a binary indicator for the primary outcome) to the

logistic regression model. This last variables was included to assess the risk of these secondary outcomes in patients who were not exposed to post-procedural antimicrobials compared to those who were exposed.

References:

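### Safe reductions are hypothesised, but no criterion for safety is stated, and the per-site safety models are too imprecise at the stated minimum volume to support the word

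*Combined protocol and SAP*

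**What the plan says.** Under Objectives, the study asks whether the intervention "can safely reduce the unnecessary use of post-procedural antimicrobials in patients undergoing urologic procedures", and the hypothesis is that "An bundled intervention across 3 hospitals will facilitate safe reductions in post-procedural antimicrobial-prescribing". Under Outcomes, two safety outcomes are defined: a late antimicrobial prescription (days 7 to 30) and a return visit for any indication within 30 days. No event rate, acceptable increase or rule for concluding safety is given for either.

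On size, the Sample Size paragraph says "This was a pilot trial, so no sample size calculation was performed". The only volume is an eligibility minimum, to "perform at least 75 qualifying procedures per year". Procedures are counted in "the 2-year baseline period or during the 1-year intervention period".

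On analysis, Statistical Methods says "Observations from each of the three sites were stratified into three data sets to accommodate separate analyses on each site". The primary model is logistic, with time, intervention phase and their interaction. Then: "To model the secondary outcomes, we used a similar approach to what is described above with the addition of a fourth explanatory variable", the fourth variable being receipt of the post-procedural antimicrobial. No model is named for the safety outcomes. This one appears to be meant for them, because the single listed secondary outcome (duration) is compared by a rank-sum test. Odds ratios are reported with 95% confidence intervals.

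**The concern.** Safety is half of the stated question, yet nothing links the planned output to an answer. Three features combine:

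- There is no margin or threshold, so no interval, however narrow, can be said to confirm or refute safety.
- Each hospital's few events must support a level change, a slope change and a baseline trend, and the three hospitals are never combined.
- The model conditions on antimicrobial receipt. That is the pathway through which withholding antimicrobials would cause harm, so the intervention coefficient is not the total effect on safety.

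The Background says the pilot could inform a larger VHA intervention. A statement that the reduction was safe would then rest on estimates compatible with both large harm and large benefit.

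**Working it through.** **There is no plan figure to reproduce.** The documents give no power, safety event rate or margin.

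**Inputs from the documents.** At least 75 procedures a year per site; 24 months before and 12 months after; one month (July 2022) omitted; separate models by site; terms for time, phase and time × phase; 95% intervals.

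**Assumptions.** Event risk 10%, varied to 15% and 20%; volume 75, 150 or 300 a year, evenly spread; flat trends; harm appearing as an immediate, sustained step; Wald test at two-sided 0.05.

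**Step 1, events at one floor-size site, 10% risk.** Before: 150 × 0.10 = 15. After: 75 × 0.10 = 7.5.

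**Step 2, precision with no true change.** The model is logit(p) = b0 + b1·t + b2·phase + b3·phase·t, with t in years from the start of the intervention phase. The average 12-month log odds ratio is b2 + b3 × (mean t in the intervention phase). Its variance comes from inverting the information matrix Σ n·p(1−p)·xxᵀ over the 36 analysed months.

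- 10% risk: SE = 0.883, interval exp(±1.96 × 0.883) = 0.18 to 5.65.
- 15% risk: SE = 0.742, interval 0.23 to 4.28.

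**Step 3, chance of missing a doubling, floor volume, 10% risk.** The odds ratio for 20% against 10% is (0.20/0.80)/(0.10/0.90) = 2.25, log 0.811. The SE under this alternative is 0.846, so z = 0.811/0.846 = 0.96. Power = Φ(0.96 − 1.96) + Φ(−0.96 − 1.96) ≈ 0.16. Missed at one site: 84%. Missed at all three: 0.84³ = 0.59, about 60%. A 1.5-fold rise is missed about 92% of the time at one site.

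**Step 4, sensitivity to volume and risk (doubling of risk).**

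| Volume per year | Risk | Missed at one site | Missed at all three |
|---|---|---|---|
| 75 | 10% | 84% | about 60% |
| 75 | 15% | 76% | 0.76³ = 44% |
| 150 | 10% | 73% | 0.73³ = 39% |
| 300 | 10% | 52% | 0.52³ = 14% |
| 300 | 20% | 14% | under 1% |

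**Step 5, does the omitted exposure term matter?** Steps 2 to 4 leave it out. Adding it, with exposure assumed to fall from 50% to 25%, still gives an 84% chance of missing a doubling at the floor with 10% risk. Testing the level-change coefficient alone in that fuller model gives 17% power, so 83% missed.

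**Step 6, pooling three floor-size sites, 10% risk (450 before, 225 after).**

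- Simple risk difference, no change: half-width 1.96 × √(0.09 × (1/450 + 1/225)) = 0.048, or 4.8 points.
- Doubling: SE = √(0.09/450 + 0.16/225) = 0.0302; 0.10/0.0302 = 3.31; power about 91%.
- 1.5-fold rise: SE = √(0.09/450 + 0.1275/225) = 0.0277; 0.05/0.0277 = 1.81; power about 44%.
- Pooled segmented model, doubling: SE about 0.488; 0.811/0.488 = 1.66; power about 38%.

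Pooling alone therefore lifts power for a doubling from 16% to 38%. The rest of the gain, to 91%, comes from dropping the trend terms.

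**The case against.** The strongest reply is that the plan contains no faulty decision rule. A reader might infer that a non-significant odds ratio will be declared safe, and that the plan would therefore nearly always return that answer. The documents do not support this. They state no rule, they report 95% intervals, and an interval of 0.18 to 5.65 in a results table would display its own imprecision. The nearly-always reading also fails on the arithmetic: even at the floor with 10% risk, at least one site would flag a doubling about 40% of the time. All of this stands, and the point made here is that a criterion is absent.

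The exposure term is a second safety contrast, so the intervention odds ratio is not the only output. That also stands. But it compares exposed with unexposed patients, without randomisation and site by site, and does not estimate what the intervention did. Its power at the floor for an odds ratio of 0.5 is 14% to 53% for event rates of 5% to 30%.

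Actual volumes and event rates are unknown, and an any-indication return visit may be common. This stands as a limit on the size of the problem: at 300 a year and 20% risk the per-site models would usually detect a doubling. The missing criterion does not depend on volume.

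Finally, this is a declared pilot. That explains the absent sample size calculation. It does not explain a hypothesis of safe reductions; a pilot can describe safety without claiming it.

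**Conclusion.** The concern holds in this form: safety is hypothesised without a criterion, and the planned per-site estimates, adjusted for exposure, are too imprecise at the only stated volume to support it. The figures of 84% per site and about 60% at all three apply to floor volume, an assumed 10% risk, a sustained doubling and one safety outcome at a time. They should not be quoted without those conditions, because they improve substantially with larger sites or commoner events. The documents do not show that non-significance would be read as safety, and that should not be attributed to the plan.

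**What to change.** For each safety outcome, add one estimate pooled over the three hospitals, stratified by site and without the exposure term: the before/after risk difference with its 95% CI. Show the trend-adjusted pooled estimate beside it. Keep the per-site models as descriptive.

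State that safe will be concluded only if the upper confidence limit is below a margin set by the sponsor. Otherwise report that safety was not established, and give the upper limit. The alternative is to reword the objective and hypothesis so that safety is descriptive. This version is dated March 2024 and implementation was in July 2022, so any margin named now should be dated and declared as prespecified or not.

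The cost is SAP wording and one table from data already to be extracted. There is a real downside. The simple difference assumes no baseline trend in events, and at floor volume and 10% risk it still misses a 1.5-fold rise about 56% of the time. The trend-adjusted pooled model misses a doubling about 62% of the time. The pilot may have to report that safety was not established.

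### The safety outcomes do not separate a repeat procedure within 30 days from a complication, and the logistic models make no allowance for repeats in one patient

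*Combined protocol and SAP*

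**What the plan says.** **Return visits** (Outcomes, Safety outcomes) are emergency department or urgent care visits, or "hospital readmission to an acute-care bed at a VHA facility for any indication within 30 days of the" "patient's index urologic procedure". Planned or staged admissions are not excepted.

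**Late prescriptions** (same section) are designated agents prescribed "by any provider within 7-30 days of the date of the patient's urologic procedure", limited to a prescription "that does not qualify as a post-procedural antimicrobial (see above"). That back-reference leads to the primary outcome, a designated agent on post-procedural day one. Nothing is said about a second procedure inside the window.

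**Eligibility** (Outcomes, Primary outcome) is worded by patient but triggered by a procedure code: "Patients will be eligible for this outcome if they underwent a medical procedure coded with a Current Procedural Terminology (CPT) code" or an ICD-10-PCS code, during "the 2-year baseline period or during the 1-year intervention period". No restriction to a first procedure is given. The word *index* is not defined. Under Eligibility criteria it is applied to the three procedure types.

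**Models** (Statistical Methods): for the primary outcome, "we used a logistic regression model and a set of three explanatory variables", fitted separately at each site. The secondary outcomes get a similar model with an added indicator for the primary outcome, and the safety outcomes appear to be covered by that sentence. No method for within-patient correlation is named.

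**The concern.** The objective is a safe reduction in prescribing, and the plan sets no margin or decision rule for safety. A null comparison on return visits or late prescriptions is therefore likely to be read as reassurance. Events that reflect a second procedure, and not harm from withholding antimicrobials after the first, add noise to that comparison. If they are equally frequent before and after the intervention, they shrink a real relative increase. Calling them non-differential is then no defence, because the shrinkage runs towards the hypothesised finding.

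The second issue is separate. Three years of code-triggered eligibility, with models described in terms of observations, most naturally allow one patient to contribute several procedures. Ordinary logistic regression treats these as unrelated, so the 95% confidence intervals may be too narrow.

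**Working it through.** The plan gives no event rate, repeat rate, correlation or power figure, so there is nothing to reproduce. The rates below are assumptions chosen to show direction and range.

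**1. Return visits, equal rate in both phases.** Let p be the true return-visit risk. Let q be the share of procedures followed within 30 days by a repeat that uses an acute bed, emergency department or urgent care, independently of true events. Observed risk = p + (1 - p)q. Take p = 10% at baseline and 20% in the intervention year, a true risk ratio of 2.0.

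| q | Baseline observed | Intervention observed | Apparent risk ratio |
|---|---|---|---|
| 1% | 10.9% | 20.8% | 1.91 |
| 2.5% | 12.25% | 22.0% | 1.80 |
| 5% | 14.5% | 24.0% | 1.66 |

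Only admitted (or emergency/urgent care) repeats enter q. If 5% of procedures have a repeat and all are admitted, the last row applies; if half are, the middle row; if a fifth are, the first. The risk difference hardly moves: 24.0 - 14.5 = 9.5 points at q = 5%, against a true 10.0.

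**2. Power per site.** The eligibility floor of 75 procedures a year gives 150 baseline and 75 intervention procedures per site, before July 2022 is omitted. For assumed true rates of 10% v 15%, the odds ratio is (0.15/0.85)/(0.10/0.90) = 1.59 and power is about 21% (two-sided 5%, simple before/after contrast without the time terms). At q = 5% the observed rates are 14.5% and 19.25%, the odds ratio is 1.41 and power is about 16%.

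**3. Return visits, rate changing between phases.** Same true rates, true odds ratio 1.59:
- q = 5% at baseline and 2% in the intervention year: observed 14.5% v 16.7%, odds ratio 1.18.
- q = 2% then 5%: observed 11.8% v 19.25%, odds ratio 1.78.

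The bias has no fixed direction.

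**4. Late prescriptions.** Let r be the share of procedures whose repeat has its day one on days 7-30 after the first procedure. Two readings of the exclusion give different answers:
- *It refers only to the procedure being scored.* A day-one prescription after the second procedure then counts as late for the first, and false events = r x day-one use. With r = 5% and assumed day-one use falling from 50% to 20-30%, false events fall from 2.5 points to 1.0-1.5 points. That could mask a real rise of 1.0-1.5 points.
- *It covers day one after any qualifying procedure.* Those prescriptions are already excluded and this differential component is zero. Other designated prescriptions tied to the second procedure, such as one issued before it, could still count.

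The text does not settle which applies.

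**5. Standard errors.** Suppose patients have one or two procedures in the same phase. The design effect is 1 + ICC x (E[m²]/E[m] - 1), and the standard error grows by its square root.
- Mean 1.1 procedures, ICC 0.1: E[m²]/E[m] = 1.3/1.1 = 1.18, design effect 1.018, factor 1.01.
- Mean 1.5 procedures, ICC 0.5: 2.5/1.5 = 1.67, design effect 1.33, factor 1.16.

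On a narrower grid (10-30% of patients with two procedures, ICC 0.05-0.5), the factor is 1.005-1.11 and the actual two-sided type I error is 5.1-7.7% instead of 5%. Repeats that straddle the two phases can act the other way on the phase contrast.

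**The case against.** The strongest case against acting has four parts.

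**All-cause return visits is a deliberate choice.** It avoids judging relatedness. Dropping admissions that carry another qualifying code could also drop unplanned re-operations for complications, which lowers the harm count. This stands, and it is why the all-cause outcome should stay and the restricted count be shown beside it.

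**Repeats may not be in the data at all.** If *index* means one procedure per patient, no within-patient correlation enters the models. This stands as a possibility. It does not remove the return-visit problem, because an admission for a second procedure would still be an event for the first.

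**Most repeats may be outpatient.** The background presents these as elective ambulatory surgeries. An outpatient repeat is not an event, so the dilution may be small. This stands as a limit on size.

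**This is an unpowered pilot at three sites.** True, but the changes need little more than procedure codes already being extracted.

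A reader might also infer more than the documents support. One such reading is that both safety outcomes are biased towards safety. For return visits that needs an equal rate in both phases. For late prescriptions, a bias that differs by phase depends on one reading of the exclusion. Another is that treating repeats as independent helps to dilute the comparison. It does not: it narrows intervals and makes a spurious signal of harm or benefit more likely.

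**Conclusion.** The point holds in limited form. The stated return-visit rule counts acute-bed admissions (or emergency or urgent care visits) for a second qualifying procedure as events for the first, whichever way *index* is read. With equal rates in both phases of 1-5%, a true risk ratio of 2.0 would appear as about 1.91-1.66; with unequal rates the direction is open. Contamination of late prescriptions by a second procedure is possible, but a bias that differs by phase is not established. If patients contribute more than one procedure, true standard errors are roughly 1-16% larger than the models report; the upper end needs half of all patients to have two procedures and an ICC of 0.5. All of these sizes rest on assumed rates and correlations.

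**What to change.** - State whether the index procedure means every qualifying procedure or one per patient, and which procedure the late-prescription exclusion refers to.
- Use patient-clustered standard errors in all logistic models. This is one software option and changes little if each patient contributes one procedure. Clustering on urologist is not advised, because separate site analyses may leave too few clusters.
- End the late-prescription window on the day before the next qualifying procedure, and show the uncut count as a sensitivity analysis. The cost is shorter follow-up after the affected procedures, which the uncut count reveals.
- Keep all-cause return visits as defined. Report beside it a count that excludes admissions for another qualifying procedure, with a note that this could also remove unplanned re-operations for complications.

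The last two changes are short programming rules on codes already drawn from the Corporate Data Warehouse. They need no new data collection.

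### The return-visit window opens at the procedure while exposure is read on day 1, so an early return visit can itself cause a patient to be coded as exposed to antimicrobials

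*Combined protocol and SAP*

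**What the plan says.** All references are to the combined protocol and SAP.

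- **Outcomes, Safety outcomes.** A return visit is "seeking care in an Emergency Department, Urgent Care Clinic or hospital readmission to an acute-care bed at a VHA facility", counted "for any indication within 30 days of the patient's index urologic procedure". There is an end day but no start day. The other safety outcome, late antimicrobial prescription, starts on day 7 and excludes prescriptions that qualify as post-procedural.
- **Outcomes, Primary outcome.** Exposure is "a prescription for a designated antimicrobial agent on post-procedural day one". Designated agents are "antimicrobial agents potentially used for a urinary tract-related indication". The stated aim is to "minimize the chance of including patients receiving antimicrobials for non-urologic or non-prophylactic indications". Nothing requires the prescription to come from the index encounter or to be issued before any return visit.
- **Statistical Methods.** The models for the secondary outcomes add "a fourth explanatory variable (a binary indicator for the primary outcome" to the time, intervention and interaction terms. The reason given is: "This last variables was included to assess the risk of these secondary outcomes in patients who were not exposed to post-procedural antimicrobials", compared with those who were.

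The only outcome under the heading Secondary outcomes is a duration. Statistical Methods compares duration by a rank-sum test, and it does not suit logistic regression. The four-variable logistic model therefore most likely applies to the two safety outcomes, although the plan does not say so.

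**The concern.** A comparison of exposed with unexposed patients needs exposure to be settled before outcomes are counted. Here the two windows overlap on days 0 and 1. Take a patient who leaves without antimicrobials, returns on the evening of the procedure or the next day with urinary symptoms, and is prescribed a urinary-tract agent on day 1. That patient can be scored as exposed with a return visit, although the visit led to the prescription.

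The direction of the error is known. Early events among untreated patients move into the exposed group, so risk with antimicrobials is overstated and risk without them is understated. The objective is to show that prescribing can be reduced safely, and the exposure term was added for that question. An error that flatters non-exposure is the unwelcome direction. Late prescriptions do not have this problem because their window starts on day 7.

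**Working it through.** The plan states no return-visit rate, power or sample size, so there is no figure of its own to reproduce. The overlap follows from the definitions; the arithmetic only illustrates its size.

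**Inputs**
- *e*, share given a planned course: 40% (assumed). For context, Background gives 37.2% for the national cohort and 55.0% as the upper quartile of hospital-level use after bladder tumour resection.
- *p*, share returning on day 0 or 1: 0.5%, 1% or 2% (assumed).
- *t*, share of otherwise untreated early returners prescribed a designated agent on day 1: 10% to 80% (assumed). The low end matters because visits count for any indication.
- *R*, return risk among all other patients: 10%, equal in both groups, so the true odds ratio is 1 (assumed).

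**Formula.** Early returners have exposure probability e + (1 − e)t; everyone else has e. The odds ratio is taken from the summed 2×2 table.

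**Worked case:** 10,000 patients, e = 40%, p = 1%, t = 50%.
- Early returners: 100. Coded exposed: 100 × (0.40 + 0.60 × 0.50) = 70. Coded unexposed: 30.
- Others: 9,900. Exposed 3,960, of whom 396 return and 3,564 do not. Unexposed 5,940, of whom 594 return and 5,346 do not.
- Odds ratio, exposed v unexposed = [(396 + 70) × 5,346] / [3,564 × (594 + 30)] = 1.12.
- With no miscoding the early returners split 40 and 60: (436 × 5,346) / (3,564 × 654) = 1.00.

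**Spurious odds ratio when the truth is 1 (e = 40%, R = 10%)**

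| Early returns | t = 10% | t = 30% | t = 50% | t = 80% |
|---|---|---|---|---|
| 0.5% | 1.01 | 1.04 | 1.06 | 1.10 |
| 1% | 1.02 | 1.07 | 1.12 | 1.20 |
| 2% | 1.04 | 1.13 | 1.23 | 1.39 |

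**Cross-check.** Let f be the share of otherwise unexposed returners who are miscoded. Then the odds ratio is [e + (1 − e)f] / [e(1 − f)]. In the worked case f = 0.01 × 0.50 / (0.01 + 0.99 × 0.10) = 0.0459, giving 0.4275 / 0.3817 = 1.12, as above.

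**Prevalence.** At 1% early returns and t from 10% to 80%, the range is 1.02 to 1.14 if e = 55% and 1.06 to 1.53 if e = 15% (assumed, should prescribing fall). The bias grows as prescribing falls.

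**Patients per site.** Sites are analysed separately. The minimum volume is 75 procedures a year, and two baseline years plus one intervention year give 225. Miscoded patients = 225 × p × 0.60 × t. At p = 1% this is 0.1 (t = 10%) to 1.1 (t = 80%); at p = 2% and t = 80% it is 2.2.

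**After the fix.** With early returners outside the exposure model, (396 × 5,346) / (3,564 × 594) = 1.00.

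**The case against.** Several points on the other side stand.

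- **Not every treated early returner is miscoded.** The agent must be a designated one and prescribed on day 1. Visits for bleeding, retention or pain may involve no antimicrobial. The claim is that such patients can be coded as exposed, not that they always are.
- **The agent list offers some protection.** It is meant to limit non-prophylactic capture. But it keeps the agents likely to be used for an early urinary complication, so the protection is partial. The prior work is cited for the list, not for a narrower exposure rule.
- **Applying the model to return visits is an inference.** It is the likeliest reading, but the plan should state it.
- **Noise dominates at a small site.** With 225 procedures, 40% exposed and 11% returning, the approximate 95% interval around an odds ratio of 1 is 0.43 to 2.35. Imprecision does not excuse bias, but the shift is small beside it.
- **The contrast is non-randomised anyway.** Confounding by indication remains whatever is done about timing.

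Two stronger readings are tempting. A reader might infer that the before/after evaluation is compromised. The documents do not support that: the time, intervention and interaction terms are touched only indirectly, through adjustment for the exposure term. A reader might also infer that a real protective effect would be hidden. In the same table, a true odds ratio of 0.80 in later returns reads 0.93 to 1.00 at 1% early returns with t from 50% to 80%, but only 0.84 to 0.88 with t from 10% to 30%. It is already 0.82 with no miscoding, because early returns were given no protective effect. Masking is possible under the stronger assumptions, but the documents hold no rates that would show it.

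**Conclusion.** The overlap is in the text, and it can bias the exposure coefficient of the return-visit model towards making non-exposure look safe. This holds on the reading that the four-variable model covers the safety outcomes. The size cannot be determined from the documents. Under the assumptions above, the spurious odds ratio lies between about 1.01 and 1.39, nearer the bottom if few early returners are given a designated agent or if baseline use is high, as is likely at top-tertile sites, and higher if prescribing falls. At a minimum-volume site it may rest on about one patient or fewer. The point is worth correcting because the direction is known and the correction is cheap, not because a large distortion has been shown.

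**What to change.** 1. State in Statistical Methods that the four-variable logistic model applies to the safety outcomes.
2. In the return-visit model that includes the exposure indicator, count visits on days 2 to 30 among patients with no return visit on days 0 or 1, so that exposure is fixed before follow-up starts.
3. Tabulate day 0 and 1 return visits by phase, and by whether an antimicrobial was prescribed before the visit, so that early failures stay visible.
4. Keep the full 30-day window for phase comparisons that do not use the exposure term.
5. State as limitations that confounding by indication remains, and that a day-1 prescription for symptoms without a counted visit is still scored as exposure.

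The cost is a few sentences and date filters on data already drawn from the Corporate Data Warehouse; the model can be rerun if analysis is complete. The ordering of prescription and visit in item 3 needs dates or times for both. The downside is that a few early visits leave the exposure comparison and appear only in the table.
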